**Table 11: Definitions**

Term	Definition
Stroke/Cerebrovascular accident (CVA)	
Rapid onset of a focal or global neurological deficit with at least one of the following: change in level of consciousness, hemiplegia, hemiparesis, numbness or sensory loss affecting one side of the body, dysphasia or aphasia, hemianopia, amaurosis fugax, or other neurological signs or symptoms consistent with stroke.
 
Duration of a focal or global neurological deficit <math>\geq 24</math> hours; OR <math>< 24</math> hours if therapeutic intervention(s) were performed (e.g., thrombolytic therapy or intracranial angioplasty); OR available neuroimaging documents a new hemorrhage or infarct; OR the neurological deficit results in death.
 
No other readily identifiable non-stroke cause for the clinical presentation (e.g., brain tumor, trauma, infection, hypoglycemia, peripheral lesion, pharmacological influences).
 
Confirmation of the diagnosis by at least one of the following: neurology or neurosurgical specialist; neuroimaging procedure (MRI or CT scan or cerebral angiography); lumbar puncture (i.e., spinal fluid analysis diagnostic of intracranial hemorrhage)

Symptomatic AF	
Required symptom(s) of AF that were experienced by the subject, made them seek medical attention, and were concurrent with a documented episode by ECG, event monitoring and/or Holter monitor. Symptoms may have included palpitations, irregular pulse (i.e. rapid, racing, pounding, fluttering, bradycardic), dizziness, weakness, chest discomfort, and breathlessness.

Thrombus	
An aggregation of blood factors, primarily platelets and fibrin with entrapment of cellular elements, frequently causing vascular obstruction at the point of its formation.

Thromboembolism	
The blockage of a blood vessel lumen by air or solid material such as device fragments, blood clot or other tissues that have migrated from another anatomic site.

Transient Ischemic Attack (TIA)	
New focal neurological deficit with rapid symptom resolution (usually 1 to 2 hours), always within 24 hours; neuroimaging without tissue injury

TREATMENT Subject	
Any subject that signs the consent form, meets eligibility criteria and has the specified study devices inserted into the body and undergoes protocol specific treatment for the intended disease.

Vagal Nerve Injury/Gastroparesis	
Vagal nerve injury is defined as injury to the vagal nerve that results in esophageal dysmotility or gastroparesis. Vagal nerve injury is considered to be a major complication if it prolongs hospitalization, requires hospitalization, or results in ongoing symptoms for more than 30 days following an ablation procedure

Vascular access complications	
Development of a hematoma, an AV fistula, or a pseudoaneurysm. A major vascular complication is defined as one that requires intervention, such as surgical repair or transfusion, prolongs the hospital stay, or requires hospital admission.

## 24.Appendices

### 24.1. *Quality of Life Instruments*

Clinical trials increasingly recognize the value of including patient reported outcome measures in their design. To understand the impact of atrial fibrillation ablation procedures on patient's quality of life, the quality of life instruments used for the trial will be the EQ-5D-5L for a generic questionnaire and the AFEQT for disease specific. Subjects will be asked to complete the questionnaires at the Enrollment visit as well as at the three, six, and 12 month follow-ups.

The EQ-5D, generic quality of life measure, will be used to assess health utilities. It is a descriptive system of health-related quality of life states consisting of five dimensions (mobility, self-care, usual activities, pain/discomfort, anxiety/depression) each of which can take one of five responses. The responses record five levels of severity (no problems/ slight problems/ moderate problems/ severe problems/ extreme problems) within a particular EQ-5D dimension.

The Atrial Fibrillation Effect on Quality of Life (AFEQT) was developed to evaluate disease-specific quality of life for patients with atrial fibrillation. The 20-item questionnaire is subdivided into three domains: symptoms, daily activities, and treatment concerns with responses provided on a seven-point Likert scale.

### 24.2. *Clinical Trial Organization*

Any Clinical Trial Organization used will be documented and available on a separate document.

1 PROTOCOL SUMMARY

1.1 Study objective

To obtain data for the Rhythmia™ Mapping System in conjunction with Boston Scientific Open-Irrigated (OI) Catheters for ablation of Paroxysmal Atrial Fibrillation (PAF) according to current international and local guidelines.

Primary objective: To assess acute and long-term outcomes for the Rhythmia Mapping System in conjunction with Boston Scientific Open-Irrigated Ablation Catheters to treat de novo Paroxysmal Atrial Fibrillation. De Novo PAF is defined as subjects undergoing first ablation procedure for PAF with no prior left atrial ablation (RF, Cryo, Surgical).

1.2 Study devices

The study will include the following Boston Scientific Open-Irrigated Catheters in geographies where commercially approved for PAF ablation:

- Blazer Open-Irrigated Ablation Catheter
- IntellaNav Open-Irrigated Ablation Catheter
- IntellaNav MiFi Open-Irrigated Ablation Catheter
- IntellaTip MiFi Open-Irrigated Ablation Catheter
- Rhythmia Mapping System Gen 1 or Rhythmia HDx, equipped with Software 1.4 or any successive commercially approved versions.
- IntellaMap Orion Catheter

1.3 Study design

INTERRUPT AF study is a prospective, non-randomized, multicenter (global), post approval clinical study (PAS).

All subjects fitting the enrollment criteria, signing the consent and undergoing the index procedure with the study devices will be followed up for three years to complete the PAS design mandated from the FDA to collect post-market data for Boston Scientific Open-Irrigated Catheters and will be followed for three years.

1.4 Follow-up visits

Study follow-up visits include Enrollment, Baseline, Index Procedure, Pre-Discharge, 1 Month, 3 Months, 6 Months, 12 Months, 24 Months, 36 Months and additional follow-up visits (including potential repeat procedures).

1.5 Planned number of sites and patients

The study will enroll 415 global subjects (US, EU, Asia-Pacific) with 25-50 centers. A minimum of 50% of the enrolling sites will be selected from the US. No study site will be allowed to contribute more than 41 subjects (10% of total allowed).

2 PURPOSE OF STATISTICAL ANALYSIS PLAN

The statistical analysis plan described in this document is to provide endpoint related analysis details to supplement the statistical methods provided in the INTERRUPT AF protocol.

3 ENDPOINTS AND ENDPOINT ANALYSES

This study has primary endpoints designed to assess the safety and effectiveness of the Boston Scientific family of Open-Irrigated Catheters in the general population of subjects undergoing de novo ablation for PAF. The study will be considered successful if both the primary safety and primary effectiveness endpoints are passed.

3.1 Primary Safety Endpoint

Safety will be evaluated by the primary safety event free rate at 12 months post procedure. Primary safety events will consist of a composite of acute primary safety events (events occurring within seven days post-procedure or hospital discharge, whichever is later), and chronic primary safety events (events occurring through 3 or 12 months post-procedure).

Acute primary safety events will be defined as the following:

- Death
- Myocardial infarction (MI)
- Vagal Nerve Injury/Gastroparesis
- Transient ischemic attack (TIA)
- Stroke/Cerebrovascular accident (CVA)
- Thromboembolism
- Pericarditis
- Cardiac tamponade/perforation
- Pneumothorax
- Vascular access complications
- Pulmonary edema/heart failure
- AV block

Chronic primary safety events will be defined as the following:

- Occurring through 3 Months post-procedure
 - Atrial esophageal fistula

- Pericardial effusion
- Occurring through 12 Months post-procedure
- Pulmonary vein stenosis (symptomatic and requiring intervention)

3.1.1 Hypotheses

The primary safety objective is to demonstrate that the primary safety event-free rate through 12 months post-procedure is greater than the specified performance goal.

H_0 : The primary safety event-free rate at 12 months post-procedure $\leq 85\%$ ^{24,25}

H_A : The primary safety event-free rate at 12 months post -procedure $> 85\%$

3.1.2 Sample size

The sample size estimate was obtained using the normal approximation to the binomial distribution and verified through simulations based on Kaplan-Meier methodology. The following assumptions were used in the sample size calculation:

Assumptions	Primary Safety
Expected rate	90% ²⁶
Performance goal	85%
Attrition (per year)	7.5%
Significance level (one-sided)	5%
Power	80%

Under the hypothesis and assumptions outlined above, the required sample size for this endpoint is 329 TREATMENT subjects.

3.1.3 Statistical methods

For the primary safety endpoint, the Kaplan-Meier 12 month (365-day) primary safety event-free rate will be calculated. Subjects who withdraw from the study prior to 12 months without experiencing an event will be censored on the date of withdrawal. The 95% one-sided lower confidence limit of the observed safety event-free rate will be compared to the performance goal of 85%. If the lower confidence limit is greater than the performance goal, the null hypothesis will be rejected. The lower confidence limit will be calculated as the pointwise confidence limit using the log-log methodology.

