### ***7.2. Withdrawal***

All subjects enrolled in the clinical study (including those withdrawn from the clinical study) shall be accounted for and documented. If a subject withdraws from the INTERRUPT AF study, the reason(s) shall be reported.

Reasons for withdrawal may include physician discretion, change in inclusion/exclusion status, subject choice to withdraw consent, lost to follow-up, or death. While study withdrawal is discouraged, subjects may withdraw from the study at any time, with or without reason, and without prejudice to further treatment. All applicable electronic case report forms (eCRFs) up to the point of subject withdrawal and an “End of Study” eCRF must be completed. For subjects who are “lost to follow-up” the investigator/center should have at least three documented attempts to contact the subject prior to completion of the “End of Study” eCRF. No additional data may be collected after a subject has been withdrawn from the study or withdraws his/her consent, for whatever reason. All open adverse events should be closed or documented as chronic. Data collected up to the point of subject withdrawal may be used. If such withdrawal is due to problems related to device safety or performance, the investigator shall ask for the subject’s permission to follow his/her status/condition.

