3.2.3 Statistical Methods

For the primary effectiveness endpoint, the Kaplan-Meier 12 month (365-day) primary effectiveness event-free rate will be calculated. Subjects who die or withdraw from the study prior to 12 months without experiencing an endpoint event will be censored on the date of death or the date of withdrawal. The 95% one-sided lower confidence limit of the observed primary effectiveness event-free rate will be compared to the performance goal of 50%. If the lower confidence limit is greater than the performance goal, the null hypothesis will be rejected. The lower confidence limit will be calculated as the pointwise confidence limit using the log-log methodology.

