5 ADDITIONAL DATA ANALYSES

5.1 Interim Analyses and Progress Report Content

No formal interim analyses are planned for the purpose of stopping the study early for declaring effectiveness or for futility. Analysis of each endpoint will be performed when all applicable data for that endpoint has been collected. Analysis of the 12-month endpoints (Primary Safety, Primary Effectiveness, Secondary Effectiveness and all additional analyses pertaining to these endpoints) will be included in a Primary Endpoint Report. Additionally, Kaplan-Meier analyses for the Primary Safety Endpoint events using all available data at the time of the report will be included in interim progress reports to the FDA. These analyses will use the same definition of safety events used in the Primary Safety Endpoint but will censor active subjects who have not experienced an endpoint event and have not completed their 12-month follow-up on the day of the data snapshot.

Progress reports will be provided to the FDA every 6 months for the first two years and annually thereafter. Reports will include sections outlined in the relevant FDA guidance pertaining to Post Approval Studies. At minimum, the progress reports will contain the following:

- Number of study sites with enrolled subjects
- Summary of subject enrollment, subject status, and demographics
- Analysis of Primary Safety Endpoint events
- Summary of adverse events, deaths, deviations, and device deficiencies

Results from the progress reports will be posted on the FDA PAS website (https://www.accessdata.fda.gov/scripts/cdrh/cfdocs/cfPMA/pma_pas.cfm).

Field Code Changed

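### The effectiveness analyses censor lost subjects at the withdrawal date, not the last date status was known, which biases the 12-month rate upward against the 50% goal

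*SAP*

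**What the plan says.** - **Censoring rule.** SAP 3.1.3 (primary safety): "Subjects who withdraw from the study prior to 12 months without experiencing an event will be censored on the date of withdrawal". Protocol 9.1.1.3, 9.1.2.3 and 9.1.3.3 carry the same sentence. For both effectiveness endpoints, SAP 3.2.3 and 3.3.3 say that event-free subjects who die or withdraw before 12 months "will be censored on the date of death or the date of withdrawal".
- **Loss to follow-up is a withdrawal.** Protocol 7.2: "Reasons for withdrawal may include physician discretion, change in inclusion/exclusion status, subject choice to withdraw consent, lost to follow-up, or death".
- **Close-out comes after the last contact.** For lost subjects, Protocol 7.2 says that "the investigator/center should have at least three documented attempts to contact the subject prior to completion of the" End of Study form.
- **No last-known-status date.** Neither document defines the withdrawal date of a lost subject, or a date on which endpoint status was last known.
- **Sensitivity analysis.** SAP 5.6.2 turns missing subjects into effectiveness events one by one. It defines missing as withdrawal or death before 12 months without an event, which is the same trigger.

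**The concern.** A subject who disappears is last observed at a visit, phone check or rhythm transmission. The withdrawal is recorded later, once attempts to reach the subject have failed. Kaplan-Meier censoring at the later date keeps the subject in the risk set, apparently event-free, while nobody is looking.

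Effectiveness is exposed because its events accrue from day 91 to day 365 and most need active detection. The schedule also leaves room for a long lag. After the six-month phone check (days 150 to 210) the next scheduled visit is at 12 months (days 335 to 395). A subject first missed at that visit may be closed out after day 365. Read literally, that subject did not withdraw before 12 months, so the rule does not censor them earlier, and they count as event-free at day 365 without a 12-month EKG or Holter.

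The study has one arm and a fixed 50% goal, so no control arm shares the bias. Primary effectiveness is one of the two tests that define study success.

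**Working it through.** **1. The plan's own sample sizes.** Take the smallest n from which exact binomial power stays at or above 80% (one-sided 5%), then divide by 1 − 0.075:
- safety, 90% against 85%: 304/0.925 = 328.6, so 329
- primary effectiveness, 60% against 50%: 169/0.925 = 182.7, so 183
- secondary effectiveness, 65% against 50%: 76/0.925 = 82.2, so 83

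All three stated figures are reproduced. None depends on the censoring date. Protocol 9.2.1 and SAP 4.1 use all eligible subjects for each endpoint, so effectiveness is checked at N = 329.

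**2. Inputs.** From the documents: attrition 7.5% a year, goal 50%, a one-sided 95% log-log limit, and events from day 91 to day 365. Assumed: 3% acute failure, constant hazard from day 91, and last contact at day 30, 90 or 180 in equal shares. The lag and the share of attrition that is loss to follow-up are varied.

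**3. Upper bound by hand.** Suppose all attrition is loss to follow-up and all of it is dated after day 365. At a true 50%:
- hazard = ln(0.97/0.50)/275 = 0.00241 per day
- event-free at day 180 = 0.97 × exp(−0.00241 × 90) = 0.781
- lost subjects with no event seen = (0.97 + 0.97 + 0.781)/3 = 0.907
- estimate = 0.925 × 0.50 + 0.075 × 0.907 = 0.5305, a bias of 3.05 points

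The standard error is about √(0.25/329) = 0.0276. The false-pass rate is about P(Z > 1.645 − 0.0305/0.0276) = P(Z > 0.54) = 29%. Simulation gives 53.0 to 53.2% and 29 to 30%.

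At a true 60% the same steps give 0.925 × 0.60 + 0.075 × 0.923 = 62.4%.

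**4. Only part of attrition dated after day 365.** The bias scales roughly with that share:
- a quarter: 0.25 × 3.05 = 0.76 points; P(Z > 1.645 − 0.0076/0.0276) = 8.5%
- a half: 0.50 × 3.05 = 1.5 points; P(Z > 1.645 − 0.0153/0.0276) = 14%

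Simulation gives about 8% and 14%. If last contact is instead uniform over the year, it gives 6.8% and 9.4%. With all attrition dated late, the range over these timing assumptions is 17 to 29%.

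**5. Lags within the year (simulation, true 50%).**

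| Lag | Rise in estimate | False passes |
|---|---|---|
| Censored at last contact | none | about 4.5 to 5% |
| 30 days, all withdrawals | about 0.2 points | 5.5 to 5.8% |
| 90 days, all withdrawals | 0.6 to 0.7 points | 6.9 to 7.5% |
| 180 days, half or all | 0.5 to 1.8 points | about 8 to 15% |

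**6. Safety.** By SAP 3.1, the acute components close at seven days or discharge and two more at three months. Only pulmonary vein stenosis runs to 12 months. Assume 85% of events by day 7, 10% on days 8 to 90 and 5% later. At a true 90%, lags of 30, 90 and 180 days on every withdrawal raise the estimate by 0.01, 0.03 and 0.05 points. At the 85% null, a 180-day lag gives 5.2% false passes against 4.9%.

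**The case against.** The strongest reply is that the key step is not in the text. Protocol 7.2 sets a minimum of contact attempts before the form is completed. It does not say that the withdrawal date is the form's completion date, and a site could enter an earlier one. Protocol 10.4.1.1 asks for at least two event-monitor transmissions a month from month 3 to month 12, with the central company following up compliance, so silence could be noticed within weeks. Subjects who withdraw consent or are withdrawn by the physician may have a real contact on that date, and the SAP censors deaths at death. The tipping-point analyses already decline to credit early withdrawals as event-free.

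Much of this stands. It makes short lags more plausible than long ones and confines the problem to loss to follow-up. It does not remove the problem. No rule ties censoring to the last transmission, so a subject who stops transmitting stays in the risk set until formally withdrawn. The tipping-point definition of missing uses the same before-12-months trigger, so a subject closed out after day 365 may escape it, and a sensitivity analysis does not alter the pass rule.

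A reader might infer that safety, including the interim reports, has the same flaw. The documents do not support that. Safety events come almost entirely early. The interim rule in SAP 5.1 applies to active subjects who "have not completed their 12-month follow-up on the day of the data snapshot". They remain under event reporting, and no formal interim stopping for effectiveness or futility is planned.

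**Conclusion.** The point holds for the primary and secondary effectiveness analyses. The direction of the bias is certain wherever a lag exists; its size is not, because the documents give neither the lag nor the share of attrition that is loss to follow-up. At 7.5% attrition, N = 329 and a true 50%:
- lags of 30 to 90 days: about 0.2 to 0.7 points and 5 to 7.5% false passes
- a quarter to a half of attrition dated after day 365: about 8 to 14% false passes, somewhat less if last contact is spread over the year
- upper bound: an estimate of 53% and about 29% false passes

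It is tempting to take the last line as the expected effect. The documents do not support that: it needs all attrition to be lost subjects, every one dated after day 365, and two-thirds last seen by day 90, before the event window opens.

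If the true rate is the planned 60%, simulated power at N = 329 is about 97% even with censoring at last contact. The harm is then a somewhat flattering estimate rather than a wrong decision. Safety is essentially unaffected.

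**What to change.** In SAP 3.2.3 and 3.3.3, and Protocol 9.1.2.3 and 9.1.3.3:
- Censor event-free subjects who are lost or withdrawn at the last date effectiveness status was ascertained, whether by visit, contact or rhythm transmission. Leave the SAP's handling of deaths as it is.
- State that this also applies when the End of Study form is dated after day 365 and there was no 12-month assessment.
- In SAP 5.6.2, count such subjects as missing.

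Use the same wording in SAP 3.1.3 and 5.6.1 for consistency, although it will hardly move the safety result. The interim rule in SAP 5.1 needs no change.

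The cost is a sentence or so per section, a slightly lower estimated rate and a slightly wider interval. The required sample size stays at 329.

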3.2 Primary Effectiveness Endpoint

The primary effectiveness endpoint will be evaluated by the primary effectiveness event-free rate at 12 months post-procedure.

Primary effectiveness events will be defined as the following:

- Acute procedural failure
- More than one repeat procedure during the blanking period (90 days post index procedure)
- Documented atrial fibrillation, or new onset of atrial flutter or atrial tachycardia event (≥ 30 seconds in duration from an event monitor or Holter Monitor, or from a 10 second 12-lead EKG) between 91 days and 365 days post index procedure
- Any of the following interventions for atrial fibrillation, or new onset of atrial flutter or atrial tachycardia between 91 days and 365 days post index procedure:
 - Repeat procedure
 - Cardioversion
 - Prescribed any AAD*

*AADs for endpoint will consist of all Class I/III and any Class II/IV medications taken for control of AF/AT/AFL recurrence

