**Table 5: Data Collection Schedule**

Data Collected	ENROLLMENT/ BASELINE		INDEX PROCEDURE (Day 0)	PRE-DISCHARGE (0-7 days post -procedure)	1-MONTH FOLLOW-UP (30±7 days)	3-MONTH FOLLOW-UP (90±30 days)	6-MONTH FOLLOW-UP (180±30 days)	12-MONTH FOLLOW-UP (365± 30 days)	24 MONTH FOLLOW-UP (730 ± 30 days)	36 MONTH FOLLOW-UP (1095 ± 30 days)	ADDITIONAL FOLLOW-UP	REPEAT PROCEDURE
Informed Consent	X											
Inclusion/Exclusion	X											
Demographic data	X											
Medical History	X											
Vitals	X		X		X			X	X	X	X	
Pre-Procedure Assessment	X											
Imaging	X a		X a		X a		X a			X a	X b	
Medication Regimen	X	X	X	X	X	X	X	X	X	X	X	X
Procedure data		X										X
EQ-5D	X				X	X	X					
AFEQT	X				X	X	X					
12-Lead EKG	X		X		X		X	X	X	X	X	
Event Monitor					X	X	X				X c	
Holter Monitor							X			X		
Documentation of Intervention for AF/AT/AFL				X	X	X	X	X	X	X	X	
Protocol Deviations	X	X	X	X	X	X	X	X	X	X	X	X
Adverse Event/Device Deficiency Reporting	X	X	X	X	X	X	X	X	X	X	X	X

a: If Pulmonary Vein Stenosis suspected or per center standard of care

b: Required for repeat procedures with non-study catheters only

c: If completed before the 12-month follow-up visit

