### ***8.14. Repeat Ablation Procedure***

It is known that a repeat ablation procedure may be necessary in certain subjects after the index ablation procedure due to recurrences of PAF or other tachyarrhythmias requiring treatment. One repeat procedure is allowed within the blanking period if considered medically necessary due to subject's intolerance of the arrhythmia. Data collection requirements for the repeat procedure are the same as those for the index procedure.

If an investigator believes it is in the subject's best interest to perform the ablation with a non-study catheter, the investigator may choose to withdraw the subject from the study prior to performing the procedure. Prior to study withdrawal and undergoing the repeat procedure with a different (non-study) catheter, imaging of the PVs is required. The appropriate type of imaging performed may be determined by the investigator. As available, the PV images must be reviewed against the pre-ablation imaging from the index procedure to rule out PV stenosis from the index ablation procedure. In addition, repeat ablation with a non-study catheter must occur  $\geq 30$  days after the previous ablation procedure.

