Acute Procedural Success is defined as pulmonary vein isolation achieved with a Boston Scientific OI ablation catheter as demonstrated by map-based entrance block with exit block and other maneuvers (such as adenosine testing) at the discretion of the physician.

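### A blanking-period rescue with a non-study catheter is never an effectiveness event: the subject is either retained and can count as a success, or withdrawn and censored

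*SAP*

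**What the plan says.** The primary event list (SAP 3.2; also Protocol 4.2, 9.1.2 and Table 11) treats blanking-period repeats as failure only for "More than one repeat procedure during the blanking period (90 days post index procedure". The secondary list (SAP 3.3; Protocol 4.3, 9.1.3, Table 11) uses the same item. Neither names a catheter.

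Protocol 8.14 states that "One repeat procedure is allowed within the blanking period". It then deals with an investigator who prefers another manufacturer's catheter: "the investigator may choose to withdraw the subject from the study prior to performing the procedure". The following sentence, on pulmonary vein imaging, describes study withdrawal and the non-study repeat as successive steps. The section adds that "repeat ablation with a non-study catheter must occur" at least 30 days after the previous ablation. The imaging footnote to Protocol Table 5 reads "Required for repeat procedures with non-study catheters only" and does not mention withdrawal.

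At the index procedure the tie to the device is explicit. SAP 3.4 says "Acute Procedural Success is defined as pulmonary vein isolation achieved with a Boston Scientific OI ablation catheter", and Protocol 7.3 classes a subject not treated with such a catheter as ATTEMPT, outside the primary endpoint analysis. SAP 3 says the primary endpoints assess this catheter family.

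On withdrawal, SAP 3.2.3 says "Subjects who die or withdraw from the study prior to 12 months without experiencing an endpoint event will be censored". Protocol 7.2 requires the reason for withdrawal to be reported and allows no data collection afterwards.

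**The concern.** Forgiving one early repeat is a deliberate allowance, and it is coherent when the repeat uses a study catheter, because the result still belongs to the catheter family under test. It is not coherent when isolation is restored with a different device. The freedom from arrhythmia then observed on days 91–365 is partly the other catheter's result, yet it enters the numerator for the study catheters.

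The withdrawal branch does not repair this. Such a subject leaves the risk set because of early recurrence, and Kaplan-Meier censoring then assumes the same later event risk as in those who remained. Both branches push the rate in the favourable direction, and an investigator's choice decides which applies.

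The planned analyses do not isolate the problem. The blanking-repeat subgroup (SAP 5.2) compares repeat with no repeat, whatever the catheter. The tipping-point analysis (SAP 5.6.2) covers withdrawn subjects as missing data, but retained subjects have complete data and are outside it.

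**Working it through.** **1. Outcome by path, as written** (for subjects with acute success at the index procedure and no other event)

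| Path | Classification | Source |
|---|---|---|
| One non-study repeat on days 30–90, retained, event-free on days 91–365 | Success | SAP 3.2; Protocol 8.14 |
| Withdrawn in the blanking period to have that repeat | Censored at withdrawal | SAP 3.2.3 |
| Any repeat for AF or new-onset AFL/AT on days 91–365, retained | Event | SAP 3.2 |
| Withdrawn after day 90 for a non-study repeat, no prior event | Censored at withdrawal | SAP 3.2.3 |

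The earliest day is 30 if the index ablation is the previous one. A second blanking repeat would already be an event, so the gap concerns the single forgiven repeat.

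**2. The plan's own figure.** Inputs from SAP 3.2.2: goal 50%, expected 60%, one-sided 5%, power 80%, attrition 7.5%. The smallest n with exact binomial power of at least 80% there and at every larger n (searched to 499) is 169, and 169/(1 − 0.075) = 182.7, so 183, as stated. The sample size is not in dispute. SAP 4.1 uses all eligible subjects, and Protocol 9.1.5 sets a minimum of 329 TREATMENT subjects, so N=329 is used below.

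**3. Pass bar at N=329** (complete data). The log-log lower limit is S^exp(1.645·se), with se = √[(1−S)/(nS)] / |ln S|.
- 180/329: S = 0.5471, se = 0.0832, limit 0.5008: pass.
- 179/329: S = 0.5441, se = 0.0829, limit 0.4978: fail.

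The bar is 180/329 = 54.7%. At the planned 60%, expected successes are 0.60 × 329 = 197, which is 17 above it.

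**4. Retained branch.** Let f be the share of TREATMENT subjects who had one non-study blanking repeat and were otherwise event-free. The documents do not give f; every value here is an assumption. The results come from a Kaplan-Meier simulation with the log-log limit, events on days 91–365, 7.5% attrition and 6,000 runs.

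| f | f × 329 | Chance of passing if the study-catheter-only rate is 50% and f is credited | Chance of passing if the as-written rate is 60% and f is recounted as events |
|---|---|---|---|
| 0 | 0 | 0.05 | 0.97 |
| 1% | 3.3 | 0.09 | 0.93 |
| 2% | 6.6 | 0.16 | 0.88 |
| 3% | 9.9 | 0.27 | 0.78 |
| 5% | 16.5 | 0.54 | 0.54 |

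**5. Withdrawal branch.** Suppose a share w withdraws in the blanking period and the others have event-free rate S. Ignoring acute failures, those subjects leave before the day-91 events begin, so Kaplan-Meier returns about S. Counting them as failures gives (1 − w)S. The difference is wS: at S = 60%, each 1% withdrawn moves the rate by about 0.6 points.

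**The case against.** The strongest reply is that the protocol expects withdrawal. The sentence after the permissive one in 8.14 presumes it, the Table 5 footnote matches that same imaging requirement, and nothing describes follow-up of a retained subject after a non-study repeat. This stands in part. A reader might infer that the protocol sets up a settled stay-in pathway; the documents do not support that, and 8.14 is ambiguous. But no text requires withdrawal, and withdrawal leads only to censoring.

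Second, these subjects had acute success with a study catheter, and a study-catheter repeat would have been forgiven too and might have succeeded. This also stands: one point per 1% of subjects is an upper bound on the misattribution, not an estimate of it.

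Third, a reader might infer a definite inflation by multiplying a blanking-repeat rate, a non-study share and a later success rate. The documents give none of the three, so no such figure can be supported. With expected successes 17 above the bar at the planned 60%, a handful of such subjects would not by itself turn a pass into a failure on expectation.

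Fourth, acute procedural failure might be read to cover the repeat. It is not defined separately, and no text extends the index criterion to repeats.

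Finally, how the sources behind the 60% expectation and 50% goal treated such repeats cannot be seen here. That is a caution about comparability, not a reason to leave the rule unstated.

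**Conclusion.** The concern holds as a gap in the endpoint rule. A blanking-period rescue with a non-study catheter yields no effectiveness event whether the subject stays or withdraws, while the index procedure is held strictly to the study catheters. The direction of bias is upward. Its size is at most 1 point per 1% of subjects in the retained branch and about 0.6 points per 1% in the withdrawal branch at a 60% rate. The illustration of 5% rising to about 16% assumes a study-catheter-only rate of exactly 50%, 2% of subjects credited, and the simulation settings above. The real frequency is undocumented and may be very small, so the documents do not show that the result will be materially inflated. The point should be settled before analysis, because the handling otherwise turns on ambiguous wording and individual choice.

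**What to change.** Add to the primary and secondary effectiveness events (SAP 3.2, 3.3; Protocol 4.2, 4.3, 9.1.2, 9.1.3, Table 11): *a repeat left atrial ablation for AF/AFL/AT with a non-study ablation catheter during the blanking period, or withdrawal in order to undergo one*. Date it on the repeat or the withdrawal, whichever is first, and apply it whether or not the subject is withdrawn. Naming withdrawal is essential: otherwise withdrawn subjects stay censored and the stay-or-withdraw choice still decides the outcome.

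Apply the same event rule to withdrawals for a non-study repeat after day 90; repeats in retained subjects on days 91–365 are already events. Keep the single blanking allowance for repeats with a study open-irrigated catheter. Reconcile the two sentences on withdrawal in Protocol 8.14; this concerns classification only and need not change clinical management. Report a sensitivity analysis under the handling as now written.

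Cost: a protocol and SAP amendment to the endpoint definitions, and possibly a slightly less favourable event-free rate. No new procedure data are needed: repeats carry the index data requirements (Protocol 8.14), which include catheter model (Protocol 8.5). The withdrawal reason is already reported (Protocol 7.2), but must be recorded specifically enough to identify this case. The stated sample sizes do not change.
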